8.5. Vital Signs

Descriptive summaries of actual values and changes from baseline will be calculated for Temperature, Systolic Blood Pressure (SBP), Diastolic Blood Pressure (DBP), Heart Rate (HR), and Respiratory Rate (RR). These summaries will be presented by visit.

A data listing of vital signs will also be provided.

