3.1. Overall Study Design and Plan

This is a multicenter, phase 3, long-term, open-label extension trial of weekly TransCon hGH in children with GHD who previously participated in a phase 3 TransCon hGH trial, i.e., Study CT-301 (heiGHt trial) or Study CT-302 (fliGHt trial). All subjects completing a prior phase 3 TransCon hGH trial who have not permanently discontinued trial medication, are without evidence of closed epiphyses, and meet all other entry criteria will be invited to participate. In general, the final visit of the prior trial should serve as the first visit of the extension trial.

Following informed consent, subjects will enter the extension trial and begin or continue TransCon hGH (depending on prior trial medication). To continue uninterrupted treatment with hGH, Day 1 (the first weekly dose) should occur on the day of Visit 1, or as soon as possible thereafter. To accommodate extension trial activities and scheduling of procedures, the weekly dosing and visit schedule may need to be adjusted as a subject enters the extension trial. In unusual situations, a period of up to approximately 6 weeks between the final visit of the prior trial and the first dose of the extension trial is acceptable. After Visit 1, subsequent visits will occur 5 days (± 1 day) post-dose at Week 13 (± 2 weeks) and then every 13 weeks (± 2 weeks) ongoing. TransCon hGH will be provided in single-use glass vials and administered with syringe and needle, initially at a strength of 12.1 mg hGH/vial and subsequently at either 12.1 mg hGH/vial or 24.2 mg hGH/vial. Once available, TransCon hGH will be supplied in DCCs for administration using a TransCon hGH auto-injector in select countries.

The trial will be conducted at approximately 100 sites specialized in the management of pediatric GHD that participated in and enrolled subjects in prior TransCon hGH trials.

Based on the subject's prior study info, he/she will be classified into one of the following treatment groups in this extension study:

- (1) Parent Study CT-302;
- (2) Parent Study CT-301 - TransCon hGH;
- (3) Parent Study CT-301 - Genotropin;

The trial consists of:

- 1) Visit 1 – the first visit of this extension trial
- 2) Treatment Period – ongoing treatment until either a) the product is approved and commercially available, b) alternative arrangements have been made for continued subject access to hGH treatment, or c) treatment for pediatric growth hormone deficiency is no longer considered appropriate

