4.2. Final Analysis

All final, planned analyses identified in this SAP will be performed after the last subject has completed the last study visit and end of study assessments, and all relevant study data have been processed and integrated into the analysis database.

5. General Statistical Considerations

All analysis will be performed based on full analysis set and summaries will be presented overall and for subjects rolling over from Study CT-301 and Study CT-302 TransCon hGH group and Genotropin group separately. Descriptive summaries will be provided where appropriate for each of the primary and secondary variables.

Continuous, quantitative (absolute values at each time point and change from baseline if applicable) variable summaries will include the number of subjects (n) with non-missing values, mean, standard deviation (SD), standard error (SE), median, minimum, and maximum, unless otherwise specified.

Categorical, qualitative, variable summaries will include the frequency and percentage of subjects who are in the particular category. In general, the denominator for the percentage calculation will be based upon the total number of subjects in the study population for the cohorts, unless otherwise specified.

All data collected on eCRF will be presented in listings.

All analysis will be performed using SAS® Software version 9.4 or later.

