5.4. Derived and Computed Variables

Table 3 provides the rules for derived and computed variables which have been initially identified as important for the analysis of the safety or efficacy as appropriate. It is expected that additional variables will be required. The SAP will not be amended for additional variables that are not related to the primary target or key secondary target variables. Any additional derived or computed variables will be identified and documented in the SAS programs that create the analysis files.

The birth date for each subject is collected on the eCRF. To be consistent with all the other TransCon hGH studies, the 15th day of the reported month is used to calculate the age and related scores. In such case, all the height SDS for the subjects will be calculated using 15th as the birth day. The HSDS reported in the eCRF will not be used as it is based on the actual birth date reported by the subject. FMD K&L will utilize the published SAS macro to calculate the height SDS and no independent QC is required for published SAS macro.

Table 3. Parameter Definition

Parameter	Definition
Annualized Height Velocity at visit x (HV) cm/year	$((\text{Height (Visit } x) - \text{Height (Visit } 1)) * 365) / (\text{Date (Visit } x) - \text{Date (Visit } 1))$ 
From the 15-month (65 weeks) visit onwards, the baseline value used for each successive HV calculation was the patient's height at the visit 52 weeks previously, e.g. height at 13 week served as the baseline value to determine HV at the 65 week ('moving 52 weeks HV basis'). If height at visit 52 weeks previously is missing then most recent height prior to the visit will be used.

Height Deviation Standardized Score (HSDS)	Height SDS will be derived using CDC 2000 (United States of America). A standard SAS program is published at: https://www.cdc.gov/nccdphp/dnpao/growthcharts/resources/sas.htm
Change from baseline	The value of each variable at each post-baseline time point minus the baseline score.
Normalized serum IGF-1 SDS	Proportion of subjects with IGF-1 Standard Deviation Score (SDS) of 0 to +2.0. Also derive for -2.0 to +2.0, -1.0 to +2.0.
Parents' Height SDS	$((\text{Parents Height}/M)^L - 1) / (L \times S)$ 
Where M=median, S= generalized coefficient of variation, and L= power in the Box-Cox transformation, the M, S, L values are obtained from the CDC website; Percentile Data Files with LMS Values

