8.4. Clinical Laboratory Evaluations

Descriptive summaries of actual (absolute) values and changes from extension study baseline values if applicable will be presented in the tables for the following by visit for the full analysis set:

- Chemistry: sodium, potassium, calcium, phosphate, chloride, total bilirubin, alkaline phosphatase, lactate dehydrogenase (LDH), aspartate aminotransferase (AST), alanine aminotransferase (ALT), gamma glutamyl transferase (GGT), albumin, total protein, creatinine, urea nitrogen, uric acid, serum iron and transferrin
- Hematology: hemoglobin, leukocytes, differential blood count of leukocytes, platelet count
- Hormone Levels: thyroid status (TSH, fT4, and fT3 levels) and morning cortisol
- Glucose Metabolism: HbA1c.
- Lipid Metabolism: Total cholesterol, triglycerides, HDL and LDL

Laboratory values will also be displayed in the data listings and those that are outside the normal range will be flagged, along with corresponding normal ranges. Any out-of-range values that are identified by the investigator as being clinically significant will be presented in a data listing.

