8.7. Other Assessments

Other safety assessments include weight, pubertal status, fundoscopy and bone age.

Weight and pubertal status are measured at each visit. Summary tables will be produced for these assessments by visit.

Fundoscopy is measured during the end of study. A listing will be presented for fundoscopy at each visit.

Bone age and delay in bone age are measured annually. Summary of the change from baseline will be presented in tables. Listing will also be provided. for bone age and delay in bone age.

9. Efficacy Analyses

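### Vital signs, weight and age-dependent laboratory values are tabulated only on the raw scale in growing children without a control arm, so normal ageing can be read as, or can hide, a small mean drug effect

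*SAP*

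**What the plan says.** **Vital signs (SAP 8.5).** "Descriptive summaries of actual values and changes from baseline will be calculated for Temperature, Systolic Blood Pressure (SBP", followed by diastolic pressure, heart rate and respiratory rate, by visit, with a listing. No percentile, SDS, age-specific limit or count of abnormal values is defined.

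**Laboratory (SAP 8.4).** "Descriptive summaries of actual (absolute) values and changes from extension study baseline values if applicable will be presented in the tables", by visit, for chemistry, hematology, hormones, HbA1c and lipids. In the listings, "those that are outside the normal range will be flagged, along with corresponding normal ranges". Values that the investigator calls clinically significant are also listed. The SAP does not say whether the ranges are specific to age and sex.

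**Weight (SAP 8.7).** "Weight and pubertal status are measured at each visit. Summary tables will be produced for these assessments by visit". Change from baseline for weight is not stated there. It follows from the general rule in SAP 5: "Continuous, quantitative (absolute values at each time point and change from baseline if applicable) variable summaries". BMI appears only among the baseline characteristics in SAP 7.1.

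**Design (SAP 3.1).** After consent, "subjects will enter the extension trial and begin or continue TransCon hGH (depending on prior trial medication". The three reporting groups differ by parent study and prior treatment, and all are on TransCon hGH. Visits run every 13 weeks with no fixed end. SAP Table 2 lists windows to Week 104 and gives a formula beyond that.

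**What is age-referenced.** Height (CDC 2000, SAP Table 3), IGF-1 and IGFBP-3 are summarised as SDS.

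**Status of these variables.** Long-term safety is the primary objective. SAP 3.3.1 and protocol 14.1.1 name vital signs and laboratory parameters as safety endpoints. Weight is not named there; SAP 8.7 treats it as another safety assessment.

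**The concern.** Blood pressure, heart rate, respiratory rate, weight and some laboratory values (for example alkaline phosphatase, creatinine and haemoglobin) are expected to move with age and puberty. That is general paediatric knowledge and not a statement in the documents. The parent trials admit children from 6 months to 17 years (protocol 5.3), and follow-up can last years. With every child on drug, a mean change by visit combines growth, ageing and any treatment effect, and nothing in the table separates them.

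Two features of the plan add to this. For most endpoints the reference is the extension baseline (SAP 5.1), when former TransCon hGH subjects are already on drug, so change from that point omits any effect already present. Subjects also leave when bone age passes 14.0 years in girls or 16.0 in boys (protocol 10.1), so the age mix behind later visit means shifts.

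At stake is whether the tables for named safety endpoints can be interpreted. A drug-related rise in systolic pressure would add to the ageing trend and could be put down to growth. A drug-related rise in heart rate would work against a falling age trend and could leave the mean unchanged.

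**Working it through.** The plan states no figure on this point. The sample size has no formula; it follows from the parent trials. The check is therefore a reading of the text plus an illustration.

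**1. Does any planned table supply an age reference?**
- SAP 8.4, 8.5 and 8.7: none.
- SAP 9.4: summaries by age category are optional and cover efficacy, baseline characteristics and TEAEs. Vital signs, weight and laboratory values are not included.
- Protocol 14.4: safety subgroups only as appropriate, and protocol 14 makes the final SAP the analysis of record.
- SAP 5.3: shift tables are mentioned in the windowing rules, but 8.4 and 8.5 specify none.

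**2. Follow-up time.** The target-day formula in SAP Table 2, 7 × 13 × (x − 1) − 1, gives day 727 for Visit 9 (Week 104). This matches the table, and 727/365.25 = 1.99 years.

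**3. Illustration for systolic pressure.** Assumptions not in the documents: drift 1-2 mmHg per year, SD 10 mmHg, within-child correlation r = 0.5, no drug effect, all subjects observed at Week 104.

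Mean change from ageing alone = drift × 2 years = +2 to +4 mmHg.

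SE of mean change = SD × √(2(1 − r)) / √n = 10 × √1 / √n = 10/√n.

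Group sizes: protocol 8 gives about 300. Protocol 5.3 gives about 150 in CT-301 randomised 2:1 (about 100 and 50) and about 150 in CT-302. Full rollover is assumed.

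| Group | n | SE (mmHg) | 2/SE | 4/SE |
|---|---|---|---|---|
| Pooled | 300 | 0.58 | 3.5 | 6.9 |
| CT-302 | 150 | 0.82 | 2.4 | 4.9 |
| CT-301 TransCon hGH | 100 | 1.00 | 2.0 | 4.0 |
| CT-301 Genotropin | 50 | 1.41 | 1.4 | 2.8 |

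SAP 3.2 expects about 400. At n = 400 the pooled SE is 0.50 and the ratios are 4 to 8.

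**4. Wider range of drift.** Let drift be 0.05 to 0.3 SD of change per year, so that the two-year mean is 0.10 to 0.60 SD and SE = 1/√n. At n = 300 the ratio is 0.10 × 17.32 = 1.7 to 0.60 × 17.32 = 10.4. At n = 400 it is 2.0 to 12.0. At the low end with n = 300, the 95% interval of −0.01 to 0.21 SD still includes zero.

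**5. Masking.** If heart rate falls 1-3 bpm per year with age (assumed), the two-year ageing change is −2 to −6 bpm. A drug-related rise of the same size gives a mean raw change of zero.

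**6. Scale of growth in the protocol's own example.** The dosing example in protocol 9.3 has a child going from 15 kg to 17 kg between visits: 2/15 = 13.3% raw increase.

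**The case against.** **Individual harm has other routes to detection.** A reader might infer that a real effect, such as fluid retention, could not be found at all. The documents do not support that. Fluid retention is a listed hGH reaction (protocol 12.1.1), physical examination and AE review occur at every visit after the first, protocol 12.1.3 gives wording for recording raised blood pressure, and SAP 8.1 tabulates TEAEs by term, intensity and relationship. This stands and limits the concern to small mean shifts. It is a partial safeguard, because mild unrelated AEs are generally not recorded, AEs are not actively solicited, and out-of-range laboratory values count as AEs only with a diagnosis, sign, symptom or need for therapy.

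**Not every group would show a clear trend.** A reader might infer an unmistakable ageing rise in each parent-study group. Under the assumptions above it is only 1.4-2.8 SE in a group of 50, and attrition before Week 104 would lower every ratio. The drift and SD are assumed and no test is planned, so these ratios describe visibility and not a decision error.

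**Laboratory data are partly handled.** Out-of-range flags exist, and protocol 15.7 has the laboratories supply reference ranges, which may already be age- and sex-specific. Not every analyte moves with age. Both points stand, but the flags are in listings and do not yield a group summary.

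**The SAP leaves room to add summaries.** SAP 5.3 presupposes shift tables, and SAP 5.4 expects further derived variables without amendment. It would be wrong to conclude that age-referenced summaries will not be produced. They are only unspecified.

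**The remedy has limits.** Height responds to treatment, so height-adjusted blood pressure could remove part of an effect. No blood-pressure or heart-rate reference is named in the documents. The LMS formula in SAP Table 3, with "Percentile Data Files with LMS Values", belongs to the parents' height row, so the precedent for the child is the CDC 2000 height SDS. These points shape the fix but do not remove the need for it.

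**Conclusion.** The point holds in a limited form. The planned summary tables for vital signs, weight and age-dependent laboratory values give raw values and raw change by visit and provide no way to separate ageing from treatment. A small mean drug effect could be mistaken for growth or be offset by it. AE tables and laboratory listings may still show individual cases.

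Under the stated assumptions, ageing alone moves mean systolic pressure by +2 to +4 mmHg by Week 104: about 3.5-7 SE pooled at n = 300 and about 1.4-2.8 SE at n = 50. The text finding does not depend on these figures; its size does. The case is strongest for vital signs and the age-dependent laboratory values, which are named safety endpoints, and weaker for weight, which is not. This is a worthwhile, inexpensive improvement to the SAP and does not invalidate the safety analysis.

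**What to change.** Keep the raw summaries and add the following.

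- **SAP 8.7:** weight SDS and BMI SDS by visit, with change from baseline, from the CDC 2000 source already used for height SDS. Confirm that the source covers the ages enrolled.
- **SAP 8.5:** systolic and diastolic pressure as age- and sex-referenced SDS or percentile from a named reference, with counts above the 95th percentile by visit. Show the height-adjusted version alongside and not instead, because height responds to treatment. Add counts of heart and respiratory rate outside named age-specific limits.
- **SAP 8.4:** baseline-to-worst shift tables against the laboratory's age- and sex-specific ranges where these exist. State in the SAP whether they do. This also gives content to the shift tables mentioned in SAP 5.3.

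No new data are needed: height and weight are measured at every scheduled visit (protocol 18.2), and sex and birth date are held. The cost is SAP wording, modest programming, and choosing blood-pressure and heart- and respiratory-rate references suitable for a multi-country trial. The SAP should say that population norms reduce confounding by age but do not replace a control arm.

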8.6. Exposure and Compliance

Summary tables for extension study will be presented for the following variables:

- Total duration of treatment
- Total number of actual doses

- Total actual dosage (mg)
- Compliance rate

The dosage (mg) is the product of the dose volume (mL) and dose concentration (mg/mL) reported in the eCRF. When there are three or more consecutive doses with more than 15% difference between actual dose and expected dose (0.24mg/kg/week), it will be considered as a dose reduction/increase. The frequency and percentages of subjects for dose not changed, dose increased or decreased will also be summarized by visit and overall.

The compliance rate will be calculated based on the rules in Section 5.4. Compliance rate will be summarized using the following categorization; <80%, ≥80%, ≥90%, ≥95% and 100%.

Listings will be presented for all exposure information.

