	
The starting dose of TransCon hGH (mg hGH/kg/week) in the extension trial will be the last dose in the prior trial, with volume or DCC presentation adjusted based on weight, if needed, at Visit 1. The weight-based dose will generally remain 0.24 mg hGH/kg/week, which is consistent with the pivotal phase 3 TransCon hGH CT-301 (heiGHt) trial. However, as the subject grows, the absolute dose (ie total milligrams of drug per week) will typically be increased accordingly, based on the TransCon hGH Bracketed Weight Table (eg From 0.35 mL to 0.41 mL, Table 1), or TransCon Dosing Table for the GH Auto-Injector and DCC Product (eg. From 7.6 mg to 9.1 mg, Table 2), as applicable.
 
Dose Adjustment Parameters:
 
The following parameters may be used by the investigator to adjust the TransCon hGH dose without Medical Expert pre-approval throughout the trial.
 
• At each visit, the TransCon hGH absolute dose may be adjusted by the investigator based on the TransCon hGH Bracketed Weight Table (Table 1), or TransCon Dosing Table for the GH Auto-Injector and DCC Product (Table 2), as applicable.• Additionally, the goal for IGF-1 should be between 0 and + 2.0 SDS (unless a different target is identified in consultation with the Medical Expert). Thus, if the IGF-1 SDS measured at a visit is < 0 SDS, the dose may be increased by approximately 20% to the next higher weight bracket by the investigator. (Although the prior requirement has been eliminated for a second [“confirmatory”] IGF-1 SDS test prior to dose titration, a second IGF-1 SDS test collected 5 days post-dose (± 1 day) remains optional at the investigator’s discretion.)• Additionally, if HV is considered to be suboptimal in an adherent subject, the dose of TransCon hGH may be increased after consultation with the Medical Expert. 
Stopping/Dose Reductions:
 
The investigator or Medical Expert may stop or reduce the dose of investigational product at any time during the trial (please notify the Medical Expert as soon as possible). For example, consideration for stopping or reducing the dose may occur in the presence of the following symptoms and laboratory abnormalities:
 
• Severe GH-related AEs at any time during the trial• Pregnancy: A subject must be discontinued from the trial if pregnant• IGF-1 > +2.0 SDS: The TransCon hGH dose may be decreased by approximately 20% to the next lower weight bracket, unless a different target SDS is identified in consultation with the Medical Expert. See Section 9.3 for details. (Although the prior requirement has been eliminated for a second [“confirmatory”] IGF-1 SDS test prior to dose titration, a second IGF-1 SDS test collected 5 days post-dose (± 1 day) remains optional at the investigator’s discretion.)

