9.5. SELECTION OF TRIAL DOSES

TransCon hGH is an inactive prodrug. The phase 2 pediatric GHD trial with TransCon hGH demonstrated that a dose of 0.21 mg hGH/kg/week provided similar hGH exposure, efficacy (annualized HV), and safety/tolerability compared to the equivalent weekly dose of Genotropin, with PD demonstrating normalization of IGF-1 SDS. This trial also demonstrated comparable tolerability and safety and numerically greater annual HV with a 0.30 mg hGH/kg/week dose of TransCon hGH. Treatment guidelines support an hGH dose of 0.24 mg hGH/kg/week ([Grimberg, 2016](#)). The TransCon hGH 0.24 mg hGH/kg/week dose is currently being studied in the phase 3 heiGHt Trial. This is also the target dose of this extension trial, however, if dose adjustments for a subject were made in the prior trial, that dose will be carried through to the extension trial. Importantly, IGF-1 levels, along with other safety parameters discussed in Section 9.6, will be measured at every visit and, if needed, changes in dosing will be allowed.

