9.6. DOSE ADJUSTMENTS

9.6.1. Dose Adjustment Parameters

The following parameters may be used by the investigator to adjust the TransCon hGH dose without Medical Expert pre-approval.

- At each visit, the TransCon hGH dose volume (vial) or DCC dose strength may be adjusted by the investigator based on the TransCon hGH Bracketed Weight Table (vial) or TransCon hGH Dosing Table for the GH Auto-Injector and DCC Product (See Section 9.3).
- Additionally, the goal for IGF-1 should be between 0 and + 2.0 SDS (unless a different target is identified in consultation with the Medical Expert). Thus, if the IGF-1 SDS measured at a visit is < 0 SDS, the dose may be increased by approximately 20% to the next higher weight bracket by the investigator (See Section 9.3) (Although the prior *requirement* has been eliminated for a second ["confirmatory"] IGF-1 SDS test prior to dose titration, a second IGF-1 SDS test collected 5 days post-dose (± 1 day) remains optional at the investigator's discretion.)
- Additionally, if HV is considered to be suboptimal in an adherent subject, the dose of TransCon hGH may be increased after consultation with the Medical Expert.

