9.6.2. Stopping/Dose Reductions

The investigator or Medical Expert (and, if needed, with the ISC review) may stop or reduce the dose of investigational product for an individual subject at any time during the trial (please notify the Medical Expert as soon as possible). For example, consideration for stopping or reducing the dose may occur in the presence of the following symptoms and laboratory abnormalities:

- Severe hGH-related AEs at any time during the trial (eg, peripheral edema, severe headache, intracranial hypertension or other adverse drug reaction and/or abnormal laboratory values).
- Pregnancy: A subject must be discontinued from the trial if pregnant.
- IGF-1 > +2.0 SDS: The TransCon hGH dose may be decreased by approximately 20% to the next lower weight bracket, unless a different target SDS is identified in consultation with the Medical Expert. See Section 9.3 for details. (Although the prior *requirement* has been eliminated for a second [“confirmatory”] IGF-1 SDS test prior to dose titration, a second IGF-1 SDS test collected 5 days post-dose (± 1 day) remains optional at the investigator’s discretion.)

Any re-establishment of the prior dose due to a subsequent sub-optimal IGF-1 response should receive prior approval by the Medical Expert.

- In those subjects who have historically been dose titrated to a bracket different than expected for weight, the investigator may—at study visits—recommend maintenance of the current absolute dose until the visit’s IGF-1 SDS values are available. Once the IGF-1 SDS values are available, the investigator may then select the most appropriate dose volume or DCC presentation.
- Evidence of hypersensitivity to TransCon hGH
- Evidence of clinically significant pre-diabetes or diabetes (HbA1c > 6.2% and an absolute increase of 0.5% from the prior visit HbA1c): Confirmation of HbA1c level is required. Once confirmed, TransCon hGH dose may be decreased to the next lower weight bracket. If appropriate follow-up monitoring shows progressively worsening glucose intolerance, additional TransCon hGH dose adjustments may be appropriate.
- Clinical evidence of BIH based on history and physical exam, including visual changes, headaches, nausea, vomiting, and/or papilledema on funduscopy: TransCon hGH treatment should be discontinued while BIH is clinically managed.

Reinstitution of TransCon hGH treatment, preferably at a lower dose, should receive prior approval by the Medical Expert.

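### SAP 8.6 judges dose changes against a flat 0.24 mg/kg/week, so a one-bracket titration can read as not changed and an untouched dose as changed (minor impact)

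*SAP*

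**What the plan says.** SAP 8.6 (Exposure and Compliance) takes runs of three or more consecutive doses with "more than 15% difference between actual dose and expected dose (0.24mg/kg/week), it will be considered as a dose reduction/increase". It then plans this summary: "The frequency and percentages of subjects for dose not changed, dose increased or decreased will also be summarized by visit and overall". It does not say which weight enters the expected dose. The same section promises listings of all exposure data.

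Protocol 9.3 tells investigators not to calculate a weight-based dose but to give the amount in the bracket table (Table 1 for vials, Table 2 for dual-chamber cartridges, DCC). Protocol 9.6.1 sets the step upward on low IGF-1: "the dose may be increased by approximately 20% to the next higher weight bracket by the investigator". Protocol 9.6.2 sets the step downward on high IGF-1: "The TransCon hGH dose may be decreased by approximately 20% to the next lower weight bracket". For children titrated off their bracket, the investigator may also "recommend maintenance of the current absolute dose" until the IGF-1 result arrives. Doses adjusted in the parent trial continue; Protocol 9.5 says "if dose adjustments for a subject were made in the prior trial, that dose will be carried through to the extension trial".

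**The concern.** The table's labels describe changes of dose. The rule behind them measures distance from 0.24 mg/kg/week. It never compares a dose with the bracket dose or with the child's previous dose. A bracket dose already drifts above and below 0.24 as weight moves across the bracket, so a step of about 20% from a favourable starting point can end inside the 15% band. A dose that nobody touched can leave the band because the child grew.

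Dose may follow IGF-1 at each visit, and long-term safety is the primary objective. How many children were off their weight bracket, and in which direction, is a basic exposure question. This is the only planned table whose labels appear to answer it.

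**Working it through.** **Inputs.** Weight brackets, volumes and concentrations from Protocol Table 1 (preferred and alternative columns, split injections summed); DCC strengths from Table 2; the 15% limit and 0.24 mg/kg/week from SAP 8.6.

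**Formula.** Deviation = dose / (0.24 × weight) − 1, where vial dose = concentration × volume. SAP 8.6 flags a deviation above +15% or below −15%. I evaluated every 0.1 kg step in each bracket.

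**1. The plan's own figure.** Protocol 9.3 gives a Table 1 average of 0.24 ± 0.02. Over the 823 table weights the preferred column has mean 0.239 and SD 0.013; the alternative column has mean 0.240 and SD 0.013. Both agree with the protocol.

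**2. Doses on their own bracket.** Deviations run from −11.0% to +10.8% (Table 1 preferred), −11.5% to +16.7% (Table 1 alternative) and −10.7% to +9.4% (Table 2). Only one weight, 5.5 kg in the alternative column, is flagged while on bracket.

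**3. One bracket, Table 1 preferred, 20.0-23.9 kg.**
- Next lower dose: 0.39 × 11 = 4.29 mg. It is flagged only above 4.29 / (0.24 × 0.85) = 21.03 kg, so a reduction is missed at 20.0-21.0 kg (11 of 40 weights, 27.5%).
- Next higher dose: 0.29 × 22 = 6.38 mg. It is flagged only below 6.38 / (0.24 × 1.15) = 23.12 kg, so an increase is missed at 23.2-23.9 kg (8 of 40, 20%).

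**4. All brackets.** Share of table weights where a one-bracket titration stays within 15%:

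| Dosing table | Reduction missed | Increase missed |
|---|---|---|
| Table 1 preferred | 271/811 = 33.4% | 198/680 = 29.1% |
| Table 1 alternative | 296/811 = 36.5% | 182/680 = 26.8% |
| Table 2 (DCC) | 281/861 = 32.6% | 269/735 = 36.6% |

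Weights with no adjacent bracket are left out. By single bracket the preferred column ranges over 24-44% for reductions and 20-38% for increases.

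**5. The protocol's example child (9.3), one bracket low at both visits.**
- 15 kg on 0.27 mL: 2.97 / (0.24 × 15) − 1 = −17.5%, *decreased*.
- 17 kg on 0.33 mL: 3.63 / (0.24 × 17) − 1 = −11.0%, *not changed*.

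His position relative to the table is the same at both visits; the label differs.

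**6. The error in the other direction.**
- Outgrown dose: 4.29 mg set correctly at 19.9 kg is at −10.2%. At 21.1 kg (a 6.0% gain) it is 4.29 / (0.24 × 21.1) − 1 = −15.3%. If it stays in place for three injections it counts as a reduction, although no dose was changed.
- Carried-over dose: a child who enters at 15 kg on 2.97 mg, unchanged from the parent trial, is at −17.5% and counts as *decreased* with no change in the extension.

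**7. The overall row.** Suppose a reduced dose is held at the same absolute amount and the child gains 2%, 5% or 8% by a later visit (assumed gains, uniform weights, each visit covering at least three doses). The share never flagged is 22.8%, 8.3% and 0% (Table 1 preferred), 26.0%, 11.3% and 1.5% (alternative), and 21.8%, 6.3% and 0% (Table 2). Increases held at the same absolute dose are not recovered: growth moves them toward 0.24, and the shares stay at 29.1%, 26.8% and 36.6%.

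**8. Would 15% against the bracket dose do?** No. Some steps are themselves under 15%: 13.3 to 15.2 mg is +14.3% (Table 2), and 9.02 to 7.70 mg is −14.6% (Table 1 preferred).

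**The case against.** The strongest reply is that SAP 8.6 gives an operational definition with a sound reference. Protocol 9.5 names 0.24 mg/kg/week as the target of this trial, and 9.3 says bracketing averages to it. The 15% limit lies above the largest on-bracket deviation in the preferred column and Table 2, and below the nominal 20% step. As a measure of departure from target the flag is defensible, and that part stands. It does not rescue labels that tell the reader whether the dose was changed.

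Three further readings are tempting and go beyond the documents:
- **A third of titrated children are misclassified.** The 27-37% is a share of table weights at one visit. Equal 0.1 kg steps put 45% of Table 1 (368/823) and 55% of Table 2 (491/886) at or above 51 kg, and the documents give no weight distribution.
- **The by-visit counts understate titration.** Missed titrations lower the counts, but outgrown and carried-over doses raise them. The documents give no frequency for either, so the net direction is unknown.
- **Comparison with the bracket would count titrations.** It shows status. The example child stays below bracket while his dose goes up, and a child restored to the bracket dose reads as on bracket although the dose was changed.

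A cost objection is that carried-over doses need parent-trial dosing data. It is weak: SAP 5.1, 7.1 and 8.2 already draw on parent-trial data, and 7.1 lists the dose and duration of prior hGH therapy.

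**Conclusion.** The point holds, with minor impact. Followed exactly, SAP 8.6 attaches labels about dose change to a quantity that does not measure dose change, and under the protocol's bracket dosing it misclassifies in both directions. No printed figure is miscalculated.

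The 27-37% assumes equal weight on each 0.1 kg step and current weight in the expected dose. Weighting by log weight or by bracket gives 24-42%. A density that falls or rises linearly across each bracket gives 8-59%. That some one-bracket titrations are missed does not depend on these choices, as the protocol's own example shows.

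The consequence is confined to one descriptive table. No endpoint or decision rule uses the flag, the overall row recovers many reductions, and the listings keep the raw doses.

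**What to change.** In SAP 8.6:
- Define *above bracket* or *below bracket* as a dose that differs, for three or more consecutive doses, from the bracket dose for the last-visit weight. Use the Table 1 column for the concentration given, or Table 2 for DCC. Put no 15% cut-off on this comparison.
- Show in a separate row the doses that are off bracket only because weight rose after they were set, or because they were carried over from the parent trial. Weight adjustment at visits is optional (Protocol 9.6.1), so this row may include doses held on purpose; a footnote can say so.
- Keep the 15% row, relabelled as departure from 0.24 mg/kg/week, and state that it uses the last-visit weight.
- Describe the new rows as off-bracket status, not as a count of titration events.

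The cost is a few sentences, a slightly longer table and a lookup in the exposure program. Relabelling the 15% row and naming the weight would alone stop the misreading, but would leave no summary of dose relative to bracket. No dosing rule changes.
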